PROTOCOL AND STATISTICAL ANALYSIS PLAN

Study Title: Cangrelor in ST-Elevation Myocardial Infarction to Decrease Infarct Size

Institution/Site:	University of Kentucky-Gill Heart Institute
Document (Approval/Update) Date:	12/13/2017
NCT Number:	NCT03043274
IRB Number	16-0990-F6A
Coversheet created:	05/22/2020

Methods:

Patients presenting with STEMI from February 2017 to February 2019 at the University of Kentucky hospitals were randomized to receive either cangrelor and ticagrelor or ticagrelor alone (standard group) before PPCI. All patients provided written informed consent approved by the institutional review board. Patients who were hemodynamically unstable with evidence of cardiogenic shock, mechanically intubated, already on dual antiplatelet therapy, or received thrombolytics were excluded. Patients received cangrelor with a dose of 30 mcg/kg bolus followed by a 4 mcg/kg/min intravenous infusion, started prior to PPCI and continued for 2 hours or for the duration of the procedure, whichever is longer. The detailed study protocol was previously reported (NCT03043274). The study was terminated because of slow recruitment. Peripheral blood (PB) samples were collected at the beginning of the PPCI procedure and before intervention (baseline), at 10-minute after starting study drug and at the end of the procedure to assess platelet aggregation in response to adenosine diphosphate (ADP) and thrombin receptor activating peptide (TRAP) using Multiplate system. Additionally, we examined circulating pro-inflammatory cells, cytokine levels, and surrogate markers for neutrophil extracellular traps (NETs), such as plasma elastase and myeloperoxidase (MPO) in the PB before PPCI, then at 6 and 12 hours after randomization using Milliplex human cytokine magnetic kit (MILLIPLEX MAP for Luminex xMap Technology, Millipore, USA) or standard ELISA kits (BD biosciences, USA) according to the manufacturer's protocol. Myocardial damage/edema (defined as myocardial tissue enhancement greater than 5 SD) were assessed using late gadolinium enhancement (LGE) on cardiac magnetic resonance at 48 hours (before hospital discharge) and at 3 months after randomization (6). Troponin I was measured during the first 12 hours after initiating the study drug.

For baseline characteristics, categorical variables were presented as frequencies and proportions and were compared using chi-square test. Continuous variables were summarized as mean with standard deviations or median with interquartile ranges as appropriate, and were compared using student T-test or Mann Whitney U test. ADP-and-TRAP-induced platelet aggregations, inflammatory cells, pro-

inflammatory cytokines, total elastase and elastase-myeloperoxidase, left ventricular ejection fraction (LVEF), and LGE-5SD were compared between both groups. All statistical analyses were performed using SPSS software (IBM SPSS Statistics for Windows, Version 24.0. Armonk, NY: IBM Corp Released 2016) and GraphPad Prism 8 (San Diego, USA).

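### Could the platelet baseline have been drawn with study drug already on board, and does the 10-minute sample have a clear time zero?

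*Combined protocol and SAP*

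**What the plan says.** All of the timing wording is in the Methods section of the combined protocol and SAP.

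- **Assignment.** Patients "were randomized to receive either cangrelor and ticagrelor or ticagrelor alone (standard group) before PPCI".
- **Cangrelor.** The infusion is "started prior to PPCI and continued for 2 hours or for the duration of the procedure". How long before PPCI it begins is not given.
- **Platelet samples.** These "samples were collected at the beginning of the PPCI procedure and before intervention (baseline), at 10-minute after starting study drug", and a third is taken when the procedure ends.
- **Inflammatory and NET markers.** These are measured "in the PB before PPCI, then at 6 and 12 hours after randomization".
- **Troponin.** "Troponin I was measured during the first 12 hours after initiating the study drug".

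The closing statistical paragraph covers baseline characteristics first. Continuous ones are summarised "as appropriate, and were compared using student T-test or Mann Whitney U test". A separate sentence then lists the outcomes, beginning with "ADP-and-TRAP-induced platelet aggregations, inflammatory cells" and ending with "LGE-5SD were compared between both groups". That sentence names no time point and gives baseline no role. Troponin is not in the list.

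The Methods also point to a fuller protocol reported under the registry number, and say that the study stopped early for slow accrual.

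**The concern.** Dosing is placed before PPCI and the baseline draw is placed at its start. Taken word for word, a patient could receive drug, reach the catheterisation laboratory and then have the baseline sample drawn, all within the rule. Platelet aggregation is the direct pharmacodynamic readout of these drugs, so even a short exposure could matter.

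Three consequences would follow if that happened. A between-arm test of the baseline would be partly a test of treatment, and a real drug effect could be taken for chance imbalance. A change from that baseline would subtract part of the effect. Adjustment for it would remove a smaller part.

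The 10-minute sample raises a second worry. It is timed from the start of study drug. The standard arm has no infusion or placebo described, and in the combination arm either of two drugs could start the clock. If the starting event differs, the 10-minute values might not be comparable between arms.

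**Working it through.** **1. The time anchors.** Let *d* be the minutes from drug start to the start of the procedure. The documents give no value. Three readings are open.

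| Reading | Baseline falls | Fit with the text |
|---|---|---|
| PPCI means the whole procedure in both sentences; *intervention* means the coronary step | *d* minutes after drug start | Allowed, but if *d* exceeds 10 the 10-minute sample precedes the baseline, against the listed order |
| *Intervention* means the study drug | Before drug | Fits the label and the order; fits the dosing sentence if PPCI there means the coronary step |
| *Intervention* and the PPCI of the dosing sentence both mean the coronary step | After procedure start, possibly before drug | The sequence procedure start, draw, drug, coronary step satisfies every sentence |

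The listed order argues against a long pre-procedure exposure, but it does not exclude a *d* under 10 minutes. The wording is therefore ambiguous. It does not show that any baseline was drawn on treatment.

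**2. What each analysis would lose.** Let δ be the between-arm difference at the later time, *f* the share of δ already present at baseline, and *r* the correlation between the two times, with equal SDs. All values of *f* and *r* are assumptions.

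- Direct comparison: estimate δ, loss 0.
- Change score: δ − *f*δ, loss *f*.
- Baseline-adjusted: δ − *rf*δ, loss *rf*.

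| *f* | Direct | Change score | Adjusted, *r* = 0.3 | *r* = 0.5 | *r* = 0.7 |
|---|---|---|---|---|---|
| 0.25 | 0% | 25% | 7.5% | 12.5% | 17.5% |
| 0.50 | 0% | 50% | 15% | 25% | 35% |

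A simulation (20,000 runs, 20 per arm, true difference 1 SD, *f* = 0.5, *r* = 0.5) retained 1.00, 0.50 and 0.75 of the effect, matching the formulas. Only the Direct column corresponds to an analysis the plan states.

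**3. If the baseline were tested by arm.** For a two-sided t-test at 0.05 with *n* per arm and a drug-related shift of *s* SD, the noncentrality is *s*√(*n*/2) on 2*n* − 2 degrees of freedom. For *n* = 20 and *s* = 0.5 it is 0.5 × √10 = 1.58 on 38 df, giving 34%. The documents give no sample size, so *n* and *s* are assumed.

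| Chance of p < 0.05 | *s* = 0.25 | *s* = 0.5 | *s* = 1.0 |
|---|---|---|---|
| *n* = 10 | 8% | 19% | 56% |
| *n* = 20 | 12% | 34% | 87% |
| *n* = 40 | 20% | 60% | 99% |

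A true pre-dose baseline would give 5%. The plan tests baseline characteristics by arm, but it lists platelet aggregation with the outcomes and does not name it as a baseline characteristic.

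**4. The clock.** Suppose time zero differed by 5 minutes between arms, an illustrative figure. That is 5/10 = 50% of the 10-minute interval. The end-of-procedure sample is not timed from drug start, so this clock does not touch it. In the standard arm ticagrelor is the only assigned drug named, so it is the natural reading of study drug. Ten minutes after each arm's own treatment start is a comparable point relative to treatment. The ambiguity that remains is which of the two drugs starts the clock in the combination arm.

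**The case for a change.** The best case for a change is that a sampling rule exists to exclude exactly this doubt. Platelet aggregation is the measure most sensitive to drug timing, a few sentences would settle the matter, and existing data could be handled from recorded dose and draw times. If the fuller protocol already contains the rule, copying it across costs nothing.

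Part of this stands. No sentence requires a pre-dose baseline, study drug is undefined, and the time points compared are not named. A reader of this document alone cannot settle these points.

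The rest carries less weight. Recruitment is over, so rewording cannot move a sample. The proposed fallback, a direct comparison at the later times, is consistent with what the plan already states. Discarding post-dose baselines patient by patient could leave values missing at different rates in the two arms, which is a cost of its own. Extending the argument to the inflammatory markers adds little, because their first sample is not called a baseline and the documents give no reason to expect a shift over the short interval before PPCI. For troponin, no between-group comparison is listed that could be affected.

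**Conclusion.** No change is needed. The timing wording is loose, but the baseline ambiguity costs the stated between-group comparison nothing at 10 minutes or at the end of the procedure. The losses of 25% to 50% for a change score and 7.5% to 35% for adjustment belong to analyses the plan does not describe, and they rest on assumed values of *f* and *r*. The inflated baseline test likewise needs an assumed shift, an assumed sample size and a baseline comparison that the plan does not list for this measure.

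The conclusion rests on two things: the plan's comparison is read as a direct one, and the document is a retrospective summary that leaves operational detail to a fuller protocol. An analyst holding the dose and draw times would recognise a post-dose sample as an on-treatment value and would know which drug started the clock. It would be a different matter if a platelet result were reported as change from baseline or adjusted for it without evidence that the baseline preceded dosing; nothing here says that was planned.

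### No use of the early platelet and inflammatory/NET values is specified; where they are shown to precede study drug, an added baseline-adjusted comparison could narrow the intervals cheaply

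*Combined protocol and SAP*

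**What the plan says.** The document has one Methods section, which closes with a statistical paragraph.

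- **Platelet aggregation.** Blood was "collected at the beginning of the PPCI procedure and before intervention (baseline), at 10-minute after starting study drug" and again at the end of the procedure: one early value and two later ones.
- **Inflammatory cells, cytokines and NET markers.** These were measured "in the PB before PPCI, then at 6 and 12 hours after randomization": again one early value and two later ones.
- **Start of treatment.** Patients were randomised to "either cangrelor and ticagrelor or ticagrelor alone (standard group) before PPCI", and cangrelor was "started prior to PPCI and continued for 2 hours" or for the length of the procedure, whichever was longer.
- **Analysis.** The statistical paragraph opens with baseline characteristics. Continuous variables there "were compared using student T-test or Mann Whitney U test". A separate sentence lists the outcomes, from "ADP-and-TRAP-induced platelet aggregations, inflammatory cells" through to "left ventricular ejection fraction (LVEF), and LGE-5SD were compared between both groups". That sentence names no test, time point, covariate or change score.
- **Context.** "The study was terminated because of slow recruitment". The number enrolled is not given. A detailed protocol is said to have been reported elsewhere; it is not among the documents reviewed.

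**The concern.** When an outcome is also measured before treatment, adjusting for that value removes the part of the between-patient variation that it predicts. The data are already in hand, and a trial stopped for slow recruitment is likely to be short of precision. The plan names only unadjusted tests for continuous variables and is silent on the early value. A reader therefore cannot tell whether the markers were compared on raw values or on change, or at which later time.

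Adjustment helps only if the early value is free of the treatment effect. Cangrelor started before PPCI, whereas the platelet baseline was drawn as PPCI began. The inflammatory sample is placed only before PPCI. Neither description fixes the order of sampling and first study drug. Adjusting for a value that cangrelor had already changed would remove part of the effect being estimated.

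**Working it through.** The plan gives no sample size, SD, effect size or correlation, so it has no figure of its own to reproduce. Everything below rests on stated assumptions.

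**Step 1. Equal SDs and the same r in both arms.** Assume n per arm, a normal outcome with SD 1, and one early value correlated r with the later value.

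- Unadjusted 95% half-width: t(0.975, 2n−2) × √(2/n).
- ANCOVA 95% half-width at one later time: t(0.975, 2n−3) × √[(2/n)(1−r²)(2n−3)/(2n−4)]. The last factor is the price of estimating the slope.

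For n = 10, unadjusted: 2.101 × √0.2 = 0.940 SD. Adjusted at r = 0.5: 2.110 × √(0.2 × 0.75 × 17/16) = 0.842 SD. For n = 20, unadjusted: 2.024 × √0.1 = 0.640 SD.

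| n per arm | Unadjusted | r = 0 | r = 0.3 | r = 0.5 | r = 0.7 |
|---|---|---|---|---|---|
| 10 | 0.940 | 0.973 | 0.928 | 0.842 | 0.695 |
| 20 | 0.640 | 0.650 | 0.620 | 0.563 | 0.464 |

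In terms of patients, the gain is 1/[(1−r²)(2n−3)/(2n−4)]. This is 1.034, 1.255 and 1.845 times at n = 10, and 1.069, 1.297 and 1.908 times at n = 20, for r = 0.3, 0.5 and 0.7.

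**Step 2. Where adjustment starts to lose.** The two half-widths are equal when 1−r² = t²(2n−2)/[t²(2n−3) × (2n−3)/(2n−4)], each t taken at 0.975 with the degrees of freedom shown. For n = 10 this is 2.101²/(2.110² × 1.0625) = 0.933, so r = 0.26. For n = 20, r = 0.17. The worst case, r = 0, widens the interval by 0.973/0.940 = 1.035 at n = 10 and 0.650/0.640 = 1.015 at n = 20.

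**Step 3. ADP aggregation during cangrelor.** A strongly suppressed response could have little spread and little relation to baseline. Assume SD 0.3 and r = 0 in the cangrelor arm, and SD 1 and correlation r in the control arm. The pooled slope is then about r/2. The residual variances are 1 − 0.75r² (control) and 0.09 + 0.25r² (cangrelor), so the large-sample variance ratio, adjusted to unadjusted, is (1.09 − 0.5r²)/1.09. That gives 0.96, 0.89 and 0.78 at r = 0.3, 0.5 and 0.7. Simulation, which includes the cost of estimating the slope, gives about 1.02, 0.94 and 0.83 at 10 per arm and 0.99, 0.92 and 0.80 at 20 per arm. The corresponding ratios under Step 1 at 10 per arm are 0.967, 0.797 and 0.542. Most of the gain disappears.

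**Step 4. If the early sample followed cangrelor.** Suppose it already carried a share f of the later effect Δ. With equal SDs the slope is r, so the adjusted effect is Δ − r·f·Δ and the share removed is r·f. At f = 0.5 this is 15%, 25% and 35% for r = 0.3, 0.5 and 0.7.

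**The case against.** The strongest reply is that no error has been shown. Randomisation makes the unadjusted comparison valid, the study title concerns infarct size, and the markers at issue are mechanistic. The size of any benefit rests on an assumed n and r: it is negligible at r = 0.3 with 10 per arm, negative below the break-even, and unavailable where timing cannot be shown. Constant SDs are doubtful for the first-named outcome, as Step 3 shows. The document is also a past-tense account of a terminated trial, so replacing its description of the comparison would misstate what was done. All of this stands. It limits the point to an added analysis and calls for standard errors that do not assume a common variance.

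A reader might infer three stronger things that the documents do not support.

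- **That the early value was not used.** The t-test and Mann-Whitney wording sits in text about baseline characteristics, the outcome sentence names no test, and the fuller protocol was not seen. The text supports only that no use is specified.
- **That the marker comparisons are biased.** Lack of adjustment costs precision; it does not bias a randomised comparison.
- **That the platelet baseline was drawn after cangrelor.** The text leaves the order open; it does not establish it either way.

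**Conclusion.** The point holds as a conditional, low-cost improvement. The plan describes an early value for each mechanistic marker and specifies no use of it. If the early value precedes study drug and r is about 0.5 or more in both arms with similar SDs, adjustment narrows the interval by about 10% at 10 per arm (0.842/0.940 = 0.90) and 12% at 20 per arm (0.563/0.640 = 0.88), and by more at r = 0.7. At r = 0.3 the gain is 1% to 3%. For ADP aggregation on cangrelor it may be slight or nil. All of these sizes depend on n, r and the SDs, none of which the documents give. LGE and LVEF are outside the point, because no pre-treatment value is described for either.

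**What to change.** 1. **Settle timing first.** For each marker, check the recorded sampling times against the time of first study drug in each arm, and report the result. State what counts as study drug in the ticagrelor-alone arm, since the text times a sample from its start without defining it there.
2. **Where the early samples preceded study drug, add an analysis and keep the reported comparison.** Suggested wording: *As a supplementary analysis, arms were compared at each later time by ANCOVA with the pre-drug value as covariate and standard errors allowing unequal variance between arms. Skewed markers were analysed on the log scale, with the log early value as covariate. The adjusted difference or geometric-mean ratio, with its 95% confidence interval, is reported at both later times for every marker.* Fit each later time separately so that each has its own baseline slope, and state how undetectable values are handled before taking logs.
3. **Where pre-drug timing cannot be shown, or times were not recorded,** do not adjust for that marker, and say so.
4. **Label the analysis post hoc** if outcome data have been seen.

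The cost is one covariate per comparison, a timing check, modest analysis work and possibly the post hoc label. No new samples are needed, and nothing changes for LGE or LVEF. If r turns out low, the adjusted interval is slightly wider, by up to 3.5% at 10 per arm under the Step 1 assumptions.

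### Does the absence of any named bleeding or other safety outcome call for a change to this plan?

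*Combined protocol and SAP*

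**What the plan says.** The Methods section gives the randomized contrast: patients "were randomized to receive either cangrelor and ticagrelor or ticagrelor alone (standard group) before PPCI". It then describes platelet function tests around the procedure, blood markers of inflammation and neutrophil activation up to 12 hours, and enhancement "on cardiac magnetic resonance at 48 hours (before hospital discharge) and at 3 months after randomization". It closes with "Troponin I was measured during the first 12 hours after initiating the study drug".

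The statistical analysis paragraph first covers baseline characteristics. It then lists the outcomes compared by arm: aggregation, inflammatory cells and cytokines, the elastase measures, and finally "left ventricular ejection fraction (LVEF), and LGE-5SD were compared between both groups".

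Three further statements bear on how the document should be read. Methods refers elsewhere for detail: "The detailed study protocol was previously reported (NCT03043274". It gives a closed enrolment period, "Patients presenting with STEMI from February 2017 to February 2019", and reports that "The study was terminated because of slow recruitment". The statistical paragraph is in the past tense: "All statistical analyses were performed using SPSS software".

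No bleeding, transfusion, adverse event, death, reinfarction or stent thrombosis outcome is named anywhere.

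**The concern.** One arm receives an extra intravenous antiplatelet drug, and platelet inhibition is itself a measured outcome. A favourable aggregation result is stronger inhibition, which is also the route by which bleeding would be expected. A document headed as a protocol and SAP that lists the benefit side of this mechanism and says nothing of the harm side looks one-sided.

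At stake is the balance of the conclusions. From this text a reader cannot tell which harms were counted, over what period, on what grading scale or in which patients. The outcome comparisons it names cannot by themselves set an effect on platelets, inflammation or infarct size beside harm in each arm.

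**Working it through.** The plan states no sample size, power, event rate or safety margin, so it has no figure to reproduce. The check is mainly a reading of the two lists side by side.

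**1. What each section names**

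| Item | Methods | Statistical paragraph |
|---|---|---|
| Platelet aggregation (ADP, TRAP) | yes | yes |
| Inflammatory cells, cytokines | yes | yes |
| Elastase and myeloperoxidase markers | yes | yes |
| Enhancement on cardiac MR | yes | yes |
| Troponin I | yes | no |
| LVEF | no | yes |
| Bleeding, adverse events, death | no | no |
| Reinfarction, stent thrombosis | no | no |

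The safety rows are empty in both columns, so the absence is confirmed for this document.

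**2. How much that absence shows.** The troponin I and LVEF rows each appear in only one column. Neither list is therefore a complete record of what was measured or compared, and an item missing from them is weak evidence that it was missing from the trial. The reference to a detailed protocol weakens it further, because that protocol is a natural place for safety definitions and cannot be consulted here.

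**3. Whether there is still a plan to amend.** Enrolment is reported as ended in February 2019, the trial as stopped, and the analyses as done. Any outcome added now would be post hoc unless the detailed protocol already specifies it. Choosing a bleeding scale before abstracting records would not restore prespecification once results are in hand.

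**4. Whether any named result is affected.** A count of bleeds does not enter the estimate or test for aggregation, inflammatory markers, LVEF or enhancement. Following the text as written makes none of these wrong.

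**5. What an added table could show.** All inputs here are assumed: n patients per arm of 10, 20 or 50, and a true bleeding rate p of 1%, 5% or 10%.

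Chance of seeing no bleed in one arm = (1 − p)^n:

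| n per arm | p = 1% | p = 5% | p = 10% |
|---|---|---|---|
| 10 | 0.904 | 0.599 | 0.349 |
| 20 | 0.818 | 0.358 | 0.122 |
| 50 | 0.605 | 0.077 | 0.005 |

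Clopper-Pearson 95% upper limit for one arm with no events = 1 − 0.025^(1/n): 0.309, 0.168 and 0.071 for n = 10, 20 and 50.

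Risk difference (cangrelor arm minus ticagrelor-alone arm), by an exact unconditional 95% interval. It inverts the score statistic with two one-sided 2.5% tests and maximizes the p-value over the nuisance rate:

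| n per arm | 0 v 0 bleeds | 2 v 0 bleeds |
|---|---|---|
| 10 | about ±0.31 | 0.20 (−0.129 to 0.556) |
| 20 | ±0.182 | 0.10 (−0.084 to 0.324) |
| 50 | ±0.073 | 0.04 (−0.035 to 0.138) |

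These figures measure the imprecision of a possible table. They do not measure any error in the present document.

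**The case for a change.** The best case for a change is that the document is titled as a protocol and SAP, so it should at least say where harm is defined. The pointer to the detailed protocol does not say that safety outcomes are found there. Troponin I, though left out of the comparison list, is at least named in Methods, whereas no harm outcome is named in either place. Early stopping makes each clinical event more informative, and a table of counts with intervals needs no new procedure and no significance test. Low precision is a reason to show intervals; it does not justify silence.

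Most of this stands as advice for the report. It does not establish a defect in the plan. The title does not alter the fact that the text describes a finished trial in brief and defers to another document. The troponin I point is fair, but LVEF shows that Methods also leaves out something that was later compared.

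The practical case is weaker than it looks. Reinfarction and stent thrombosis are ischaemic events that an antiplatelet drug may reduce, so placing them in a harm table would mix efficacy with safety. Follow-up to discharge varies in length between patients. No blinding or adjudication is described, bleeds may not be charted in gradable form, and abstracting records after closure may need access and approval that the documents do not address.

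**Conclusion.** No change to the plan follows. The observation is correct as a statement about this document: no safety outcome is named in either section, although the arms differ by an added intravenous antiplatelet drug. It is a gap in an abridged, retrospective account, and the people reporting the trial can fill it sensibly. They can point to the detailed protocol where it defines safety outcomes, and give bleeding and deaths by randomized arm, described as post hoc if they were not prespecified.

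The size of the gap cannot be determined, because the documents give neither a sample size nor an event rate. Under the assumed 10 to 50 per arm, even a table with no bleeds would leave differences of roughly 31 to 7 percentage points in either direction unexcluded. Adding one would therefore settle little about safety, and it would not alter any platelet, inflammatory or infarct-size comparison.

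This rests on two things: that the detailed protocol was not available for this review and may cover harms, and that the text describes a closed and analysed trial. If the detailed protocol proved silent on harms, the omission would be a weakness of the trial's design, but an edit to this finished account could not repair it.
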